## 9.7 Study Stopping Rules

In a case of critical non-compliance of site to the Code of Federal Regulation (Title 21, CFR Part 312); the study protocol; the Declaration of Helsinki; or any applicable regulation, the Sponsor may stop the entire study or participation of a study site at any time. In addition, the Sponsor may stop the entire study, or terminate participation of a study site for any medical reason at any time.

In the event of individual subject's premature study termination resulting from an AE, refer to [Section 12.6](#).

### Premature termination of a subject

A subject must be terminated from the study if any of the following occur:

- Withdrawal of informed consent.
- Treatment with any other investigational product in another clinical study.
- Treatment with any BoNT other than study medication.
- Pregnancy detected at Screening or Baseline.
- Any significant treatment-related side effects where study continuation would constitute an unacceptably high risk for the subject.

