#### 4.1 Schedule of Study Procedures and Assessments

Procedures and assessments	Screening  (Day -14 to 0)	Randomization  (Baseline, Day 0)	Week 1 (± 2 days)	Week 2 (± 5 days)	Week 4 (± 2 days)	Week 8 (± 5 days)	Week 12 (± 5 days)	Week 16 (± 5 days) End of Study 
Visit No	1	2	3	4	5	6	7	8
Informed consent	x							
Inclusion/exclusion criteria	x	x 						
Medical history	x							
Demographics	x							
Pregnancy test 	x	x			x 	x 	x 	x
Physical examination	x							x
Vital signs 	x	x	x		x		x	x
Concomitant medication	x	x	x	x	x	x	x	x
GLS-I 	x	x	x	x	x	x	x	x
GLS-S 	x	x	x	x	x	x	x	x
Photography 		x		x	x		x	x
Treatment satisfaction 					x		x	x
IMP administration		x						
Post-treatment obs./AE & AESI assessment 		x						
AE and AESI  assessment		x	x	x	x	x	x	x
Subject diary		D	R/D	R				

1. Screening and Baseline, including randomization and treatment, can be done on the same day. If Screening and Baseline are done on the same day, assessments only need to be performed once.
2. For subjects that are prematurely discontinued from the study (at any time), the End of Study visit will take place within one week of discontinuation.
3. If Screening and Baseline are done on different days, the following inclusion and exclusion criteria are to be re-confirmed at Baseline: investigator and subject assessment of glabellar line severity at maximum frown using GLS-I and GLS-S, respectively, as well as documentation of medical history, concomitant medications and AEs.
4. Pregnancy testing for all women of childbearing potential: Screening, Baseline (if Screening and Baseline are done on different days), and End of Study. All pregnancy testing will be urine dip stick testing.
5. Additional pregnancy testing (urine dipstick) for women of childbearing potential in Austrian sites, only.
6. Vital signs include blood pressure (diastolic /systolic) and pulse.
7. Investigator's assessment of glabellar line severity at maximum frown and at rest. Assessment will be made using the 4-point GLS-I: (0 =none, 1=mild, 2=moderate, 3=severe). Results will be recorded in the eCRF.
8. Subject's assessment of glabellar line severity at maximum frown and at rest. Assessment will be made using the 4-point GLS-S: (0 =none, 1=mild, 2=moderate, 3=severe). Results will be recorded in the eCRF.

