### 9.3.2 End of Study Visit

The End of Study visit is planned to take place 16 weeks after treatment.

For subjects who are prematurely discontinued from the study (at any time), the End of Study visit will take place within one week of discontinuation.

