### 10.3 Withdrawal and Discontinuation

A subject may voluntarily withdraw from study participation and data collection for any reason at any time (withdraw consent). A subject will be considered lost to follow-up after at least three unsuccessful phone calls have been made and one certified letter has been sent, in an attempt to contact the subject. All efforts to contact the subject must be documented.

Every effort will be made to have the withdrawn/discontinued subject complete the End of Study visit ([Section 9.3.2](#)). The reason for withdrawal/discontinuation will be recorded on the eCRF ([Section 12.6](#)).

In the event of an AE/AESI/SAE, clinical and/or laboratory investigations that are beyond the scope of the required study procedures may be performed as part of the evaluation of the event. Any subject with an AE, AESI, or SAE will be evaluated by the investigator and will be treated and/or followed up until the symptoms return to normal or acceptable levels, as judged by the investigator.

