 A time deviation of ± 5 days is allowed for each visit, except for the Week 1/Visit 3, and Week 4/Visit 5 visits, where deviations of ± 2 day are permitted. Sites must adhere to the schedule of events and visit windows and subjects must ensure they are available for those visits. Any deviation from the visit schedule and its associated time windows will still be documented as a protocol deviation.

 Screening and Baseline, including randomization and treatment, can be done on the same day. If Screening and Baseline are done on the same day, assessments only need to be performed once.

Pregnancy testing on all applicable subjects must be repeated at the Baseline Visit if Screening and Baseline assessments are not done on the same day.

 If Screening and Baseline are done on different days, the following inclusion and exclusion criteria are to be re-confirmed at Baseline: GLS-I and GLS-S for investigator and subject, respectively, and concomitant medications.

 AESI assessment at Visit 2, Day 0 to be done prior to treatment. AESI Questioning: active questioning by guided review of systems as per AESI manual. If an AESI is reported, a targeted physical examination around the area of the reported AESI must follow.

 Subjects will be monitored for AEs 30 minutes after administration of the IMP. 30-minute post IMP administration, general, non-leading AE questioning as well as active AESI questioning must be performed.

 For subjects that are prematurely discontinued from the study (at any time), the End of Study visit will take place within one week of discontinuation. For subjects terminating the study early as per decision made at a site visit, the study procedures required at the End of Study visit should be performed at the visit during which the subject was terminated from the study.

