### 2.2 Secondary Objectives

1. To assess the percentage of responders (FWS score of 0 or 1 and a  $\geq 1$  point reduction in FWS score at maximum frown) after a single treatment with BoNT/A-DP compared to a single treatment of [REDACTED] at Weeks 1, 2, 8, 12 and 16, based on investigator and subject assessments.
2. To assess the percentage of responders (FWS score of 0 or 1 and a  $\geq 2$  point reduction in FWS score at maximum frown) after a single treatment with BoNT/A-DP compared to a single treatment of [REDACTED] at Weeks 1, 2, 4, 8, 12 and 16, based on independent investigator and subject assessments.
3. To assess the percentage of responders (FWS score of 0 or 1 and a  $\geq 1$  point reduction in FWS score at rest) after a single treatment with BoNT/A-DP compared to a single treatment of [REDACTED] at Weeks 1, 2, 4, 8, 12 and 16, based on independent investigator and subject assessments.
4. To assess time to onset of effect after a single treatment with BoNT/A-DP compared to a single treatment of [REDACTED], as measured at Weeks 1, 2, and 4, based on independent investigator and subject assessments.
5. To assess the duration of effect in subjects who respond after a single treatment with BoNT/A-DP or a single treatment of [REDACTED], based on independent investigator and subject assessments.
6. To assess treatment satisfaction at Weeks 4, 12, and 16 using FACE-Q Satisfaction with Outcome Scale.
7. To determine the safety and presence of any adverse effects of a single treatment of BoNT/A-DP compared to a single treatment of [REDACTED] in the treatment of glabellar lines.

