### 7.2 Handling of Missing Data

#### 7.2.1 Missing Data Analysis Methods

Analyses will be performed by visit. The main analysis will be performed based on all available data. That is, no imputation of missing values will be conducted (e.g., no last observation carried forward), except for estimating the response rate at Week 4 for the co-primary endpoints where subjects with missing FWS assessments at Baseline or Week 4 will be considered as non-responders.

For all other visits and endpoints, summary statistics will be based on observed data.

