# Statistical Analysis Plan (SAP)

## 11 APPENDICES

### Appendix A - Visit Window

Analyses will be performed by nominal visit, irrespective of any time window deviations. For the End of Study (EOS) visit, the following criteria will be applied:

- The nominal visit will be used throughout for all subjects who have not discontinued.
- For discontinued subjects, the EOS data will be assumed to be the preceding visit where no assessments are available.
- For discontinued subjects, the EOS data will be assumed to be the visit following the preceding visit if for the preceding visit an assessment is already available.
- Unless duplicate records are present in the database, there should be no duplicate data per visit.

The following examples illustrate the approach:

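### The SAP has no rule for scores taken after a non-study botulinum toxin, so another product's effect can count as study-drug response at late visits

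*Protocol*

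**What the plan says.** Protocol 9.7 lists "Treatment with any BoNT other than study medication" among the events after which a subject must leave the study. Protocol 14.10 prohibits other botulinum toxin for any reason but attaches no consequence for the data.

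On follow-up, Protocol 9.3.2 says: "For subjects who are prematurely discontinued from the study (at any time), the End of Study visit will take place within one week of discontinuation". Section 10.3 is softer: "Every effort will be made to have the withdrawn/discontinued subject complete the End of Study visit". Under section 12.6, a subject who does not return keeps the last scores under the last visit attended. Where termination is decided at a site visit, a footnote to Table 12-1 says that "the study procedures required at the End of Study visit should be performed at the visit during which the subject was terminated from the study". Those procedures include GLS-I, GLS-S and FACE-Q.

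SAP Appendix A assigns a discontinued subject's End of Study (EOS) data to the preceding scheduled visit if that visit is empty. If it already holds an assessment, "the EOS data will be assumed to be the visit following the preceding visit". SAP 7.2.1 adds: "The main analysis will be performed based on all available data". In SAP 8.6.3 only a missing score makes a subject a non-responder. Loss of effect is a return to the individual Baseline grade or worse in a Week 4 responder, and subjects without a loss are censored at the last visit with a score at maximum frown.

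Other toxin use is not mentioned in the FAS definition (SAP 6.2), the four a priori major deviations (SAP 6.3) or the changes from protocol (SAP 9). There is no per-protocol set.

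**The concern.** The secondary objectives concern a single study treatment. The SAP's fifth is "To assess the duration of effect in subjects who respond after a single treatment with BoNT/A-DP or a single treatment of" the comparator, and duration of effect is in the study title. Protocol 7.1 says that function usually recovers in two to three months and that repeat injection is needed to maintain the effect, while follow-up runs to 16 weeks. A subject whose effect fades in that period may obtain another toxin. The protocol foresees this by naming it as a termination event.

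The EOS visit then follows within a week of discontinuation, not of the injection, so the new toxin may already be acting. The trial itself looks for onset daily in the first two weeks. If the score is 0 or 1, the plan credits it to the study product. The late responder rates and the duration curve of that arm are then too favourable. FACE-Q is exposed in the same way, because the form asks about the most recent procedure, which would be the other product.

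**Working it through.** **The plan's own figure.** SAP 5 gives n = 100 per group, 81.5% in both groups and a two-sided 95% interval. Half-width = 1.96 × √(2 × 0.815 × 0.185 / 100) = 1.96 × 0.0549 = 0.1076, or 10.8 points. The figure reproduces and is not in dispute.

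**How the rules route the score.**
- Week 12 attended, other toxin at Week 13, EOS about Week 14: the preceding visit is filled, so the scores are filed as Week 16.
- Week 8 attended, other toxin at Week 10, EOS about Week 11: filed as Week 12.
- Week 12 missed, other toxin at Week 13: the preceding visit is empty, so the scores are filed as Week 12, and Week 16 is missing.

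In each case the score is observed. It stands in both the non-responder analysis and the observed-values analysis.

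**Visit responder rate.** One subject of 100 is 1.0 point. That is a ceiling: the subject must attend, score 0 or 1, and otherwise have been a non-responder at the mapped visit. To illustrate, assume a true late rate of 40/100 in both arms and k such subjects in one arm only (Newcombe intervals, in percentage points):

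| k | Difference | 95% CI |
|---|---|---|
| 0 | 0.0 | −13.35 to 13.35 |
| 1 | 1.0 | −12.40 to 14.35 |
| 2 | 2.0 | −11.44 to 15.34 |
| 5 | 5.0 | −8.57 to 18.31 |

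The 40% rate, the counts and the one-arm split are all assumptions. Equal numbers in both arms would raise both rates and leave the difference unchanged.

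**Duration: who is exposed.** Entry requires a Baseline score of 2 or 3. Take a Week 4 responder who is a non-responder at the last visit before the other toxin:
- Baseline 2: the score is at least 2, so the loss is already recorded.
- Baseline 3, score 3: the loss is already recorded.
- Baseline 3, score 2: neither a responder nor a loss. This subject is exposed.

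The other exposed group is subjects still responding at the last visit whose effect fades before the next one.

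**Duration: illustration.** Assume 80 Week 4 responders, with 8, 34 and 18 losses at days 57, 85 and 113 and 20 censored at day 113.
- S(57) = 72/80 = 0.900.
- S(85) = 0.900 × 38/72 = 0.475, so the median is day 85.
- If k of the day-85 losses are instead censored at an EOS visit on day 78, S(85) = 0.900 × 38/(72 − k). This is 0.489 for k = 2, 0.510 for k = 5 and 0.534 for k = 8. The median moves to day 113 for k = 5 and k = 8.
- If the 5 are counted as losses on day 78, S(78) = 0.900 × 67/72 = 0.8375 and S(85) = 0.8375 × 38/67 = 0.475, as at the start.

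**The case against.** Several points on the other side stand.

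- A reader might infer that every terminated subject must yield a contaminated score. The EOS visit depends on every effort being made, and the scores of a subject who does not return stay at the last visit attended. The later visit is then already a non-response in the non-responder analysis.
- A reader might infer that each such subject both adds a point and turns a loss into a censored time. The three cases above show that most subjects who had visibly faded at a scheduled visit already have a loss on record.
- The jump in the median from day 85 to day 113 is not evidence of size. The assumed curve sits at 0.475, just under one half, so a change of 3.5 points moves the median by a whole visit.
- Other toxin may be rare: planned use is an exclusion and use during the study is prohibited. That it would occur more in one arm and hide a true difference is conjecture. The documents give neither rate.
- Toxin given elsewhere for another indication also triggers termination but need not change the glabellar score.
- The blinded data review meeting can still class the event as major.

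Two replies remain. The intent-to-treat wording in the FAS settles which arm a subject belongs to. It does not say that another product's effect is part of the effect of a single study treatment. And the review meeting assigns analysis sets and classifies deviations, but has no rule for setting individual scores aside. That the analyses are exploratory lowers the stakes without making the late estimates right.

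**Conclusion.** The gap is real. Following the written rules, a score of 0 or 1 produced by another toxin counts as study-drug response, usually at Week 12 or 16. The size is at most 1 percentage point per affected subject at 100 per arm, under the three conditions above. One to five subjects, all in one arm, would shift a late difference by 1 to 5 points, but those counts are assumed. Duration is affected only where effect faded between visits or partly.

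The documents do not support the stronger reading that the main result is compromised. EOS data could be mapped to Week 4 in principle, but other toxin would have to be used before the study drug's effect would be expected to wear off, so the co-primary endpoints are practically unaffected. The direction of any bias between arms is not known. This should be settled before unblinding because the correction is simple and would otherwise be chosen with arm-level data in view.

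**What to change.** Leave the termination rule unchanged. Before unblinding, add to the SAP:

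- **8.6.3 and Appendix A:** FWS and FACE-Q data collected on or after a non-study botulinum toxin that could affect the glabellar lines are not used as study-drug effect and are not mapped to a visit. Whether it could do so is judged blinded at the data review meeting, from the recorded indication, route and date.
- **Responder endpoints:** the subject is a non-responder at that and later visits in the non-responder analysis, and missing in the observed-values analysis.
- **Duration:** keep the stated loss definition and censor at the last FWS before the other toxin. As a sensitivity analysis, count loss on the toxin date.
- **6.3:** list the event as a major deviation. Safety data stay in.

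The sensitivity analysis should be reported beside the main one. In the illustration above, moving the censoring time from day 78 back to day 57 still gives S(85) = 0.900 × 38/67 = 0.510. Only counting the losses returns 0.475.

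The cost is a few lines of text. Protocol 14.10 already has the indication, route and dates recorded. A partial toxin date should be queried, because SAP 7.2.2.2 would move it to the first of the month or year and could discard valid earlier scores. Late responder rates may be slightly lower.

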### Premature termination of a site or of the entire study

A site or the entire study may be terminated if any of the following occur:

- Critical non-compliance to Title 21, CFR Part 312; the study protocol; the Declaration of Helsinki; or any applicable regulation.
- The positive benefit/risk ratio is no longer maintained.
- The Sponsor may stop the entire study for any medical reason at any time.

- The Sponsor can terminate the study or a study site at any time for any other reason.

## 10. SUBJECT SELECTION, WITHDRAWAL AND DISCONTINUATION

### 10.1 Inclusion Criteria

Subjects who meet **ALL** of the following criteria are eligible for this study:

- 18 - 75 years of age, inclusive, at the time of Screening.
- Has moderate to severe glabellar frown lines at maximum frown (severity score of 2 or 3 on GLS-I/GLS-S) as determined in-clinic assessments by both the investigator and subject (where: 0='none', 1='mild', 2='moderate', 3='severe').
- Subject has a stable medical condition with no uncontrolled systemic disease.
- Female subjects of childbearing potential must test negative for pregnancy and agree to use highly effective birth control during the course of the study.
- Subjects who wear glasses must be able to adequately self-assess the severity of their glabellar lines (according to the GLS-S), without glasses obstructing the forehead area.

### 10.2 Exclusion Criteria

Subjects who meet **ANY** of the following criteria are **NOT** eligible for this study:

- Previous treatment with any serotype of botulinum toxin for any indication within the 12 months prior to Screening, or any planned treatment with botulinum toxin of any serotype for any reason during the study (other than the investigational treatment).
- Known hypersensitivity to either study medication or its excipients.
- Any medical condition that may place the subject at increased risk due to exposure to botulinum toxin, including diagnosed myasthenia gravis, Eaton-Lambert syndrome, amyotrophic lateral sclerosis, profound atrophy or weakness in the target muscles, or any other condition (at the investigator's discretion) that might interfere with neuromuscular function or contraindicate botulinum toxin therapy.
- Facial laser or light treatment, microdermabrasion, superficial peels or retinoid therapy within the three months prior to Screening or planned during the study.
  - Apart from the procedures specified above, previous treatment with any facial aesthetic procedure in the glabellar area (including chemical peeling, injection with biodegradable fillers, photo-rejuvenation) within 12 months prior to Screening or planned during the study.
- Previous insertion of permanent material in the glabellar area, or planned insertion during the study.
- Any planned or history of surgery in the glabellar area and/or canthal line area, or scars in the glabellar and/or canthal line.
- Active skin disease/infection or irritation at the treatment area.

- Inability to substantially lessen glabellar frown lines and or lateral canthal lines even by physically spreading them apart.
- Use of a muscle relaxant within two weeks prior to Screening, or planned use during the study.
- Marked facial asymmetry or ptosis of eyelid and/or eyebrow, or current facial palsy or neuromuscular junction disorders as judged by the investigator.
- Pregnant, breastfeeding or planning to become pregnant during the study.
- Use of prohibited medication including anticholinergic drugs, or drugs which could interfere with neuromuscular function, including aminoglycoside antibiotics and curare-like compounds within two weeks prior to Screening or planned during the study.
- Planned surgery with general anesthetic (use of local anesthetic outside the glabellar area is permitted).
- Participation in another clinical study within one month of Screening and throughout the study.
- Previous participation in another botulinum toxin aesthetic study which involved the treatment of glabellar lines in combination with canthal lines and/or forehead lines in the previous 18 months.
- Chronic drug or alcohol abuse (as per investigator discretion).

### 10.3 Withdrawal and Discontinuation

A subject may voluntarily withdraw from study participation and data collection for any reason at any time (withdraw consent). A subject will be considered lost to follow-up after at least three unsuccessful phone calls have been made and one certified letter has been sent, in an attempt to contact the subject. All efforts to contact the subject must be documented.

Every effort will be made to have the withdrawn/discontinued subject complete the End of Study visit ([Section 9.3.2](#)). The reason for withdrawal/discontinuation will be recorded on the eCRF ([Section 12.6](#)).

In the event of an AE/AESI/SAE, clinical and/or laboratory investigations that are beyond the scope of the required study procedures may be performed as part of the evaluation of the event. Any subject with an AE, AESI, or SAE will be evaluated by the investigator and will be treated and/or followed up until the symptoms return to normal or acceptable levels, as judged by the investigator.

